1.0 Objectives

1.1 Purpose:

The overarching goal of this study is to advance research on family-based prevention of negative child outcomes for reintegrating Operation Enduring Freedom/Operation Iraqi Freedom personnel by evaluating different formats of a parenting program, After Deployment, Adaptive Parenting Tools/ADAPT. The ADAPT program is based upon the Parent Management Training-Oregon Model/PMTO, but adapted for military deployed families. We will examine which of three delivery formats of ADAPT is most effective at reducing youth risk behaviors associated with negative childhood outcomes by improving parenting, child, and parent adjustment. There is a clear intent to benefit all subjects in this study (except surveyed teachers), including children.

We will conduct a three-group, two-site randomized trial to test the comparative effectiveness of ADAPT delivery approaches. The study will randomly allocate 360 NGR families to one of three conditions: (i) group-based web-enhanced ADAPT; (ii) individualized web-facilitated ADAPT; or (iii) self-directed web ADAPT.

Thus, specific aims are as follows:

1. Conduct a three-group, two-site randomized trial to test the comparative effectiveness of ADAPT delivery approaches
 - a. Families will complete a pre-intervention baseline assessment and post-intervention follow-up assessments at 6, 12- and 24 months.
2. Test the generalizability of ADAPT effectiveness across three delivery approaches using intent to treat (ITT) analyses
 - a. Test the value-added impact of group-based delivery relative to facilitated and self-directed web approaches
 - b. Comparative effectiveness will be tested by specifying a non-equivalence hypothesis for group based and individualized facilitated relative to self-directed web only

We hypothesize that (1) individualized web-facilitated parenting intervention will be equally effective as the group-based web-enhanced intervention, and (2) both individualized and group-based ADAPT will be more effective than a self-directed web-condition. Effective internet delivery methods will facilitate development of new approaches to engage military families separated by deployment, isolated by geographical location, and in need of strategies to deal with deployment and reintegration stressors, directly addressing limitations and barriers to access to evidence based prevention programs.

PROTOCOL TITLE: Comparing Web, Group, and Telehealth Formats of a Military Parenting Program

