identify the model that best characterizes patterns of growth. We can also specify an additional nonlinear quadratic factor, a higher order polynomial function to capture any nonlinearity. Accelerated or decelerated change would be specified with loadings fixed at 0, 1, 4, and 16. A sequential set of models tests the latent variances and model fit across a random intercept, linear growth, and quadratic model to determine the optimal growth pattern. The comparative effectiveness hypothesis for observed parenting is shown in Figure 2 as linear growth. Group Based and Web Facilitated will be contrasted to the Self-Directed omitted group. Analyses will test that the Group Based effect ($\beta_1 > 0$) and the Web Facilitated ($\beta_2 > 0$) will show greater 2-year improvements relative to Self-Directed. For the LGM in Figure 2 we estimated power using Mplus Monte Carlo simulations with 1000 replications. An advantage of this approach is the ability to incorporate specific patterns of expected attrition over time. For the figure in Figure 3, contrasts for Group Based and Web Facilitated were fixed at a mean of .33 and variance of .22 representing the random allocation across groups. The latent initial status intercept and latent growth factors were specified reflecting a commonly observed ratio of 5:1 for the variance components (Initial Status $\psi_2 = .5$ and SD = .70; and Linear Growth $\psi_2 = .1$, SD = .31). The effect size (ES) is then the ratio of group contrast mean differences in the latent growth factor divided by the SD for growth. A sample size of 306 (cumulative attrition of 15% over 2 years, specified as .05, .10 and .15 over time) obtained power of .98 respectively to detect small effects (ES=.10) for β_1 and β_2 relative to Self-Directed and likewise for child, couple, parent adjustment.

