Analyses for Hypothesis 2 of Aim 1. To test whether the ADAPT Group Based and Web Facilitated have similar effects we will employ two related approaches to test whether ($\beta_1 = \beta_2$) for the paths shown in Figure 2. First, using the same model specification shown in Figure 2, we will further specify equality constraints in the LGM model to directly compare the relative magnitude of β_1 and β_2 . Second, we will conduct a one-sided non-inferiority test (i.e., a test of equivalence) for the intent to treat growth slope factor means and variances for the respective parenting, child, couple, and parent adjustment constructs; hypothesizing no differences between the Group Based and Web Facilitated conditions. We used the non-inferiority module in the Power Analysis and Sample Size program for the equivalence test of means using two one-sided tests for two groups of 102 (Group Based and Web Facilitated). The study is powered .82 using a .05 one-sided alpha when the reference mean = 1 and the comparison mean = 1, and the range of difference still results in the conclusion of equal means when the comparison group is plus or minus a quarter of a standard deviation of the reference mean ($\pm .25$ SDs). Finally, we will also examine dosage, participation, and variation in fidelity as potential moderators of group intervention effects.

PROTOCOL TITLE: Comparing Web, Group, and Telehealth Formats of a Military

Parenting Program

VERSION DATE: May 4, 2018

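### The stated power of .82 for the Hypothesis 2 equivalence test does not follow from its inputs: 102 per arm at ±.25 SD gives about .11 with two one-sided tests, or about .55 with a single non-inferiority test

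*Protocol*

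**What the plan says.** Section 1.1 of the Protocol hypothesises that the "individualized web-facilitated parenting intervention will be equally effective as the group-based web-enhanced intervention". Under Analyses for Hypothesis 2 of Aim 1 it plans two approaches: equality constraints on β1 and β2 in the latent growth model, and a "one-sided non-inferiority test (i.e., a test of equivalence) for the intent to treat growth slope factor means and variances".

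The power statement for the second approach reads: "We used the non-inferiority module in the Power Analysis and Sample Size program for the equivalence test of means using two one-sided tests". It is for two groups of 102, and continues: "The study is powered .82 using a .05 one-sided alpha when the reference mean = 1 and the comparison mean = 1". Equal means are still to be concluded when the comparison group lies "plus or minus a quarter of a standard deviation of the reference mean", which the text then gives as ±.25 SDs.

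The section gives no raw SD, baseline-outcome correlation or other precision gain for this calculation. Section 17.2 repeats only the pre-post power and does not return to this test.

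**The concern.** With about 100 families per arm, a quarter of a standard deviation is a narrow equivalence margin. The 90% confidence interval for a difference between two such groups is almost as wide as the whole margin, so power of .82 at a true difference of zero is implausible on its face. The text also treats non-inferiority and equivalence as one test. They answer different questions and differ in power by a factor of about five here.

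Equal effectiveness of these two formats is one of the trial's two hypotheses. If the power is far below .82, an inconclusive result is the likely outcome even when the formats are identical, and readers have been told otherwise. The equality constraint does not fill the gap. In a simple two-group comparison with 102 per arm, a true difference of .25 SD is detected with power of only .427 (two-sided .05), so it is non-significant about 57% of the time. A non-significant constraint therefore says little about equality.

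**Working it through.** **Inputs** (all from section 1.1)
- n = 102 per arm: 120 randomised per arm less 15% attrition, 120 × .85 = 102; equally 306 / 3.
- One-sided alpha .05; true difference 1 − 1 = 0; margin .25 SD.

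**Attempt to reproduce .82.** The margin is in SD units, so set SD = 1.
- Standard error = √(2/102) = .1400.
- Margin / standard error = .25 / .1400 = 1.785.
- 1.785 − 1.645 = .140.
- Two one-sided tests: 2Φ(.140) − 1 = .112 (normal). With the t distribution on 202 df, averaging over the sample variance, .109; simulation .108.
- Single non-inferiority test: Φ(.140) = .556 (normal). Noncentral t .554; simulation .553.

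Put as a confidence interval, the 90% half-width is 1.652 × .1400 = .231 SD. Equivalence can be declared only if the observed difference falls within about .25 − .231 = .019 SD of zero.

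**What .82 would need**

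| | Two one-sided tests | Single non-inferiority test |
|---|---|---|
| Power at 102 per arm, .25 SD | .11 | .55 |
| Power at 120 per arm (no attrition), .25 SD | .23 | .61 |
| Margin for .82 at 102 per arm | ±.42 SD | .36 SD |
| n per arm for .82 at .25 SD | 286 | 211 (210 by the normal formula) |

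**Possible origins of .82.** Each changes a stated input or adds an unstated one.
- Raw margin .25, SD .70 (the initial-status SD in the Follow Up Analyses paragraph), single test: .25 / (.70 × .1400) = 2.551; Φ(2.551 − 1.645) = .817 (t: .815). This is a margin of .25 / .70 = .36 SD and one test, not two. Two one-sided tests with the same inputs give .63.
- Raw margin .25 with SD about .60 (a value not in the document), two one-sided tests: .817 (t: .813), a margin of .25 / .60 = .42 SD.
- Margin on the raw-outcome SD with baseline adjustment, residual SD = √(1 − r²), r assumed. Two one-sided tests give .32 at r = .5 and .60 at r = .7, and reach .82 only at about r = .80. A single test reaches .80 at r = .7.

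**Which SD.** The test is applied to growth slope factors. For its own effect size, the Follow Up Analyses paragraph scales by the slope SD: "The effect size (ES) is then the ratio of group contrast mean differences in the latent growth factor divided by the SD for growth". The Hypothesis 2 text does not say whether its margin uses that SD or the raw-outcome SD. On the slope scale power stays low. With that paragraph's variances (.5 and .1) and an assumed residual variance of .1, it is about .05 for two one-sided tests if the arms may differ at baseline and intercept and slope are uncorrelated. It is about .12 with equal baselines and a negative intercept-slope correlation. These last figures are illustrative only.

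**The case against.** The strongest reply is that the power may be right and the labels wrong. The text names a non-inferiority module and a one-sided alpha, and enters raw means of 1. A raw margin of .25 with the documented SD of .70 and one test gives .815 to .817, close to .82. This is a plausible origin. But it contradicts both the ±.25 SD margin and the statement that two one-sided tests were used, and .70 is the SD of initial status whereas the planned test concerns slopes. What stands is that margin, test and power are mutually inconsistent, and the document does not show which of them was misreported.

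Second, .11 belongs to a simple two-group comparison of means, whereas the planned analysis is a repeated-measures growth model that could be more precise. That is fair: .11 is what the stated calculation yields and does not predict the final model's power. However, the .82 is presented as a two-group means calculation, with no precision gain stated. If one was assumed, it has to be written down.

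Third, the decision rule for equivalence and the reading of the equality constraint may be left to the SAP. That is accepted. The mismatch does not depend on either.

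**Conclusion.** The concern holds. On the stated inputs the power is .11 for two one-sided tests or .55 for a single non-inferiority test, against a stated .82: an overstatement of .71 or .27. This rests only on the protocol's own figures (102 per arm, one-sided alpha .05, zero true difference, ±.25 SD) and on the margin and the test sharing one SD. Nothing elsewhere in the protocol repairs it. The baseline-correlation and slope-scale figures rest on assumed values, and the conclusion does not need them. Since the figure supports one of the trial's two hypotheses, it must be corrected.

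**What to change.** In section 1.1, Analyses for Hypothesis 2 of Aim 1:

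1. Name one test. If the conclusion is to be that the formats are equally effective, it should be the two one-sided tests procedure.
2. State which SD scales the margin: the slope-factor SD or the raw-outcome SD.
3. Make power, margin and assumptions agree. For example: with 102 families per arm, a true difference of 0 and one-sided alpha .05 for each test, power is about .11 at ±.25 SD, and .82 is reached only at about ±.42 SD. If a wider margin was intended, state it and justify it. If a precision gain was assumed, document it and give the recomputed power for β1 − β2 under the growth model.
4. State here or in the SAP that equality is concluded only if the 90% confidence interval for β1 − β2 lies wholly inside the margin, that the result is otherwise inconclusive, and that a non-significant equality constraint is not by itself evidence of equality.

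If the simulation model in the Follow Up Analyses paragraph is used for item 3, check its settings first. It reports power of .98 for an effect of .10 slope SD. Even with slopes measured without error, 102 per arm gives .10 / .140 = .71 standard errors, a two-sided power of about .11.

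The cost is one rerun of the power calculation, some rewording and probably a less favourable stated power. No extra families or data are needed.

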Follow Up Analyses. For the intent to treat (ITT) analyses of long term follow up, we will specify latent growth models (LGM) recommended for long term effectiveness designs involving maximum likelihood SEM. LGMs have become more standard because they more reliably assess change. Growth models combine individual and group levels of analysis, taking into account mean growth and individual variation. Fixed effects (e.g., random assignment to ADAPT, parent and child gender) and time-varying random effects may be estimated using chronometric time weights. A model specifying an initial status latent variable (assessing variance in BL differences) and a linear slope latent variable (estimating individual differences in change over time), would be specified using factor weights of 1, 1, 1, 1, for the respective repeated measures, and factor weights of 0, 1, 2, and 4 for growth. The first step in LGM is to

PROTOCOL TITLE: Comparing Web, Group, and Telehealth Formats of a Military Parenting Program

VERSION DATE: May 4, 2018

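### The Hypothesis 2 margin is a quarter of an SD that the protocol does not name, and the stated power of .82 does not follow from that margin with 102 families per arm

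*Protocol*

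**What the plan says.** The Hypothesis 2 analysis is in Protocol section 1.1, under Analyses for Hypothesis 2 of Aim 1. Besides an equality constraint in the growth model, it plans a test "for the intent to treat growth slope factor means and variances for the respective parenting, child, couple, and parent adjustment constructs". That test is introduced as one-sided non-inferiority and glossed as equivalence. The power calculation that follows is described as two one-sided tests for two groups of 102.

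On power it says: "The study is powered .82 using a .05 one-sided alpha", "when the reference mean = 1 and the comparison mean = 1". Equality is still concluded when "the comparison group is plus or minus a quarter of a standard deviation of the reference mean", and a parenthesis gives the margin as ±.25 SDs. No SD value accompanies the means of 1.

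Under Follow Up Analyses in the same section, the growth model uses "factor weights of 0, 1, 2, and 4 for growth" at baseline, 6, 12 and 24 months, so one slope unit is the change per 6 months. Two latent SDs are given: .70 for initial status (variance .5) and .31 for linear growth (variance .1). The Hypothesis 1 effect size is the slope contrast "divided by the SD for growth". Nothing there refers to the Hypothesis 2 margin. Section 17.2 repeats only the pre-post power statement, so the .82 appears in one place.

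**The concern.** The margin decides whether the two facilitated formats may be called equally effective, which is one of the trial's two hypotheses. A margin of a quarter of an SD is a definite rule only if the SD is identified and belongs to the quantity being tested. Here the tested quantity is a slope, the SD is unnamed, and the model contains two candidates that differ by more than a factor of two. If this stays open, the choice could be made after the slopes are known.

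The stated power ought to settle which SD was meant, but it does not fit the natural reading. A reader who accepts .82 would expect the trial to have a good chance of confirming equivalence if the two formats are truly alike. If the true figure is far lower, failure to show equivalence would say little about the formats.

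**Working it through.** **Inputs** (all Protocol section 1.1)
- 102 per arm, from 120 × .85.
- One-sided alpha .05, so z = 1.645.
- True difference 0 (both means set to 1).
- Margin ±.25 SD.
- Growth SD .31 (√.1 = .316) and initial-status SD .70 (√.5 = .707).

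**Formulas** (normal approximation)
- SE of the difference = SD × √(2/102) = .1400 × SD.
- One-sided non-inferiority: power = Φ(margin/SE − 1.645).
- Two one-sided tests: power = 2Φ(margin/SE − 1.645) − 1.

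**1. The plan's figure as worded.** If one SD sets both the margin and the variance, it cancels: margin/SE = .25/.1400 = 1.785, and 1.785 − 1.645 = .140.
- Non-inferiority: Φ(.140) = .556 (.554 by noncentral t).
- Two one-sided tests: 2 × .556 − 1 = .112 (.108 by t).

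Neither is .82, whichever SD is meant. For .82 with 102 per arm the margin would have to be (1.645 + .915) × .1400 = .36 SD for non-inferiority, or (1.645 + 1.341) × .1400 = .42 SD for two one-sided tests. Keeping .25 SD would need 2 × (2.560/.25)² ≈ 210 or 2 × (2.986/.25)² ≈ 286 per arm.

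**2. What does return about .82.** Treat .25 as raw units.

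| SD used | margin/SE | Non-inferiority | Two one-sided tests |
|---|---|---|---|
| .70 (initial status) | .25/.0980 = 2.551 | .817 | .635 |
| .71 (between groups, pre-post ANOVA) | .25/.0994 = 2.515 | .808 | .615 |
| .31 (growth) | .25/.0434 = 5.76 | 1.00 | 1.00 |

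The closest match is one-sided non-inferiority on the initial-status SD. Two one-sided tests with a raw .25 reach .82 at an SD of about .60, which the protocol does not contain.

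**3. Size of the ambiguity.** The slope margin is .25 × .31 = .078 (.079 with √.1) or .25 × .70 = .175 (.177 with √.5). The ratio is .70/.31 = 2.3. Multiplied by 4, the 24-month differences allowed are about .32 and .71 raw, or .45 and 1.0 initial-status SD.

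Take a true slope difference of .25 growth SD (.079), error-free slopes with SE = √(.1 × 2/102) = .0443, and two one-sided tests. The chance of declaring equality is:
- growth-SD margin: Φ(−1.645) + Φ(.158/.0443 − 1.645) − 1 ≈ .02;
- initial-status margin: Φ(.098/.0443 − 1.645) + Φ(.256/.0443 − 1.645) − 1 ≈ .71.

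**4. Measurement error.** The protocol gives no residual variance, so a range is assumed: .25 to 1.0, with complete data at times 0, 1, 2, 4. The sum of squared deviations of the times is 8.75, so the slope variance becomes .1 + σ²/8.75.
- At σ² = .25, SE = √(2 × .1286/102) = .0502 and 1.645 × SE = .083. This exceeds the .079 margin, so two one-sided tests could not declare equivalence. Non-inferiority power is Φ(.079/.0502 − 1.645) ≈ .47.
- At σ² = 1.0, SE = .0648 and non-inferiority power is about .34.

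Over the same range the .71 in step 3 falls to between .62 and .43.

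**The case against.** The strongest reply is that the rule can be read without difficulty. The parenthesis gives the unit as SDs, the test is stated to be on the slope factor, and Follow Up Analyses already standardises slope contrasts by the growth SD. A quarter of .31 is therefore the obvious margin, and a statistical analysis plan could confirm it in a line. Much of this stands. A reader might infer that the margin has no unit at all; the text does not support that, since the unit is an SD and only its identity is missing.

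A reader might also apply a raw .25 to the slope, which would be .25/.078 = 3.2 times the growth-SD margin. The words do not support that either: they say .25 SDs, and the 1 in the power sentence is a mean. The documented spread is that between the two latent SDs.

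The inference about a level-scale calculation is also limited. The match with .82 holds only for one-sided non-inferiority. Under two one-sided tests, the form in which the power calculation is described, the same inputs give .63.

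The reply does not rescue the power figure. The more natural the growth-SD reading, the plainer it is that .82 cannot belong to it. Attrition does not explain the gap: with all 120 per arm, a .25 SD margin gives .615 or .229. Nor can this be left to the analysis plan, because the protocol itself fixes the margin and states the power.

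**Conclusion.** The point holds in two parts. First, the protocol does not name the SD that scales the Hypothesis 2 margin, and its two latent SDs give slope margins of about .08 and .18, a 2.3-fold difference. Second, the stated power of .82 is not delivered by a ±.25 SD margin with 102 per arm: it is about .55 for one-sided non-inferiority and .11 for two one-sided tests. The second part is the firmer, because it does not depend on which SD was meant, only on the same SD setting margin and variance. Both figures are upper values, since they assume error-free slopes and a true difference of 0.

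A reader might go further and conclude that the margin was in fact set on the level scale and then moved to the slope. The arithmetic makes that plausible under one of the two tests named, but the protocol does not say so. The pass rates of .02 and .71 rest on the planning variances and error-free slopes, and show only that the choice of SD matters.

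**What to change.** In section 1.1, Analyses for Hypothesis 2 of Aim 1:
- State the margin as .25 × the growth-factor SD, the SD that already defines the effect size under Follow Up Analyses. Beside it give the slope value (about .08 per 6 months) and the implied 24-month difference (about .32 raw on planning values). Say whether the SD is fixed in advance or estimated.
- Say whether the test is one-sided non-inferiority or two one-sided tests.
- Replace .82 with the power for that test, margin and SD at 102 per arm: at most about .55 or .11, less once a residual variance is assumed.

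This needs no new data or families. The cost is a much less favourable power statement. The sponsor must accept that the test as specified has low power, so that failure to show equivalence will be uninformative. If a wider margin is preferred, it should be fixed and justified in slope units before the slopes are seen.

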2.0 Background

2.1 Significance of Research Question/Purpose:

Combat deployment and related challenges are family stressors, associated with more negative parent-child interactions, ineffective and coercive parenting practices and lower levels of parenting satisfaction (e.g. Glenn et al., 2002; Jordan et al., 1992; Samper, Taft, King, & King, 2004).

Disrupted parenting practices are well-known predictors of risk for child adjustment difficulties that are precursors to youth substance use, including behavior problems, school failure, deviant peer association, and depression (Patterson & Fisher, 2002; Sanders, Cann, & Markie-Dadds, 2003). These child adjustment problems can contribute to continuing parental stress, increasing parental distress, and further disrupting parenting ([name] & Forgatch, 2004).

2.2 Preliminary Data:

With funding from NIH, the first adaptation of PMTO for military families was initiated by this research team, and is currently being evaluated in a randomized controlled trial/RCT of 400 reintegrating primarily National Guard and Reserve/NGR families with preliminary effectiveness. Known as After Deployment, Adaptive Parenting Tools/ADAPT, the program is a 14-week group-based parenting intervention with an online supplement. ADAPT addresses issues specific to deployment and combat stressors, enhances ecological validity by incorporating examples and materials relevant to NGR families, and addresses psychological and environmental barriers to accessing services. In addition to PMTO skills, ADAPT adds a mindfulness and emotion coaching component based on the hypothesis that the immediate reactivity and suppression of emotions learned on the battlefield may spill over at home following reintegration, leading to dys-regulated emotional interactions that increase family coercion. Preliminary data show improved parenting practices, mindfulness, parenting efficacy, and couple adjustment for ADAPT compared with controls ([name], 2013). The After Deployment, Adaptive Parenting Tools/ADAPT study is the only military parenting study of school-aged children to date with preliminary evidence from an RCT. We propose to address existing gaps in access to services by NGR families by testing the comparative effectiveness of different formats of this program including in-person, online, and telehealth.

2.3 Existing Literature:

PMTO is a well-established empirically supported intervention targeting highly stressed parents that applies Social Interaction Learning theory (SIL, Patterson, Chamberlain & Reid, 1982). Similar to family stress and stress amplification models (e.g., Elder Jr, Van Nguyen, & Caspi, 1985), SIL posits that parenting mediates the effects of family stressors on child adjustment. That is, deployment and related stressors would be expected to impair social interactional patterns, leading to increases in coercion, decrements in positive parenting, and increased risk for child maladjustment. PMTO interventions have demonstrated efficacy

PROTOCOL TITLE: Comparing Web, Group, and Telehealth Formats of a Military Parenting Program

VERSION DATE: May 4, 2018

and effectiveness, showing benefits for children including reductions in behavior problems that are precursors to substance use, actual substance use, and internalizing problems, as well as increases in social competence and school adjustment (for a comprehensive overview see Forgatch & Patterson, *in press*). Moreover, recent findings indicate that strengthening parenting practices contributes to improved outcomes for parents themselves (Patterson, Forgatch, & [name], 2010).

